6.4.2.11 Findings resulting from skin monitoring

Findings resulting from skin monitoring will be analyzed descriptively by treatment group. All subjects who consent for safety follow-up and attend the safety closeout visit will undergo a thorough skin examination by a dermatology expert. The information will be recorded on the eCRF assigned to the safety closeout visit. The analysis will show the number of subjects who consented to participate in the Safety Follow-up, how many were assessed by a dermatologist or other clinician, which diagnostic tests were used and the results of the assessment as follows: number of normal and abnormal findings; and following an abnormal finding which type of abnormality as recorded in the eCRF: 'Precancerous skin lesion', 'Cutaneous sarcoma', 'Other malignant skin tumor' and 'Other skin abnormality'.

Relevant cases will be reported as AEs, potentially as an AESI (pre-cancerous and malignant skin lesions). Malignant skin tumors will be classified as SAEs. Narratives will be written for skin-related AESI and SAEs.

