If the cyst resolution does not occur, then the length of time between the start of the episode and the last observation will be considered the cyst episode duration.

If only the start of the episode is recorded but no follow-up has been performed, then the duration of the episode is unknown.

The analysis will include cysts episodes occurring in both ovaries with no distinction of ovary laterality (left or right). Although the information of ovary laterality will not be displayed in the table, it will be critical to monitor the progression of individual cyst like structures.

The Intervals A and B (acc to Figure 4–1) will be considered. Therefore, two sets of tables will be produced. Ovarian cyst episodes will be assigned to the time interval when the start of the episode occurs.

Two analyses will be produced for ovarian cyst episodes:

- Number of subjects with at least one ovarian cyst episode by time intervals.
- Number of ovarian cyst episodes by time intervals including: i) descriptive statistics of ovarian cyst episode duration, ii) by categorization of the duration by 4-week intervals, and iii) descriptive statistics of largest diameter of the cyst like structure per episode and per time interval.

Two tables will be produced for these two analyses, one for each definition of cyst episode resolution.

The analysis of AEs originating from ovarian cysts will include AEs identified by the Bayer MedDRA query (BMQ) for 'Benign ovarian cyst and associated complications' [V21], which include the preferred terms (PTs): Haemorrhagic ovarian cyst, Ovarian cyst, Ovarian cyst ruptured and Ovarian cyst torsion.

The table will show number of subjects with AEs, non-serious AEs and serious AEs (SAEs). For each one of these AE categories the table will include severity, whether the AE led to drug withdrawal (if applicable) and AE duration. In addition, SAEs will include the reason for being classified as serious as recorded in the eCRF.

The analysis will be done for pre-treatment AEs, TEAEs and post-treatment AEs. Pretreatment and post-treatment AEs will be shown by treatment group (including pooled group A1+B2) only. TEAEs will be shown by treatment group for TP1, TP2 and overall, and additionally they will be shown by study drug. AEs with onset during a treatment period or up to 8 days after last study drug intake in any treatment period will be considered 'on-

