6.4.2.4 Adverse events

All AEs will be coded by MedDRA terms (the current version at the time of analysis) and classified into pre-treatment AEs, treatment-emergent (TEAE) and post-treatment AEs.

AEs will be flagged as TEAE except for AEs for which there is clear evidence that the AE starts before date of first study drug intake (pre-treatment AEs) or after the date of last study drug intake + 60 days (post-treatment AEs).

AEs with clear evidence of start before the date of first study drug intake are flagged as pretreatment AE unless the AE worsens at or after the date of first study drug intake and before or at the date of last study drug intake + 60 days. AEs starting before but worsening at or after the date of first study drug intake and before or at the date of last study drug intake + 60 days will be considered as two AEs, a pre-treatment AE and a TEAE. The pre-treatment AE will end at the date of worsening and the new TEAE will start at the date of worsening.

Same applies in case an AE starts at or after the date of first study drug intake, but before the date of last study drug intake + 60 days and worsens afterwards, then e.g. leading to a TEAE and a post-treatment AE.

Worsening of an AE is defined as follows:

- AE intensity/grade is worsened (e.g., moderate to severe)
- AE changed to a serious event
- AE ends with death
- AE is drug-related

TEAEs will further be categorized into on-treatment and off-treatment events.

TEAEs will be flagged as on-treatment except for TEAEs where there is clear evidence that the TEAE starts outside all on-treatment phases. Each on-treatment phase starts with the date of first study drug intake and ends with the date of last study drug intake during a treatment period plus 8 days. TEAEs with clear evidence of start outside all on-treatment phases will be flagged as off-treatment TEAEs unless the TEAE worsens during an on-treatment phase. TEAEs starting during off/on-treatment phase, but worsening during an on/off-treatment phase will be considered as two TEAEs, an off/on-treatment TEAE and an on/off-treatment TEAE. The off/on-treatment TEAE will end at the time of worsening and the on/off-treatment TEAE will start at the time of worsening.

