Descriptive analysis will be performed (i) by treatment group for both TP1 and TP2 combined, (ii) by treatment group (including pooled treatment group A1+B2) separately for each treatment period and (iii) by study drug for both TP1 and TP2 combined. The tabulation will follow in principle the Bayer Global Standard Tables catalogue (currently V 4.0), with the necessary modifications like for on- and off-treatment TEAEs.

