6.4.2.4.1 Assignment to study drug

Depending on the TEAE onset, the AE will be assigned to a study drug. This is relevant for subjects with switch in study drug (i.e., treatment groups B1 and B2), as it may not be clear whether the TEAE is assigned to the study drug given in TP1 or to the study drug given in TP2.

- AEs with an onset before the start of TP2 will be assigned to the study drug given in TP1.
- AEs with an onset at or after the start of TP2 will be assigned to the study drug taken during TP2.

Consequently, AEs with an onset before start of TP2 which are ongoing during TP2 will not be assigned to the study drug given in TP2 unless the TEAE worsens after start of TP2. In case it is not clear to which study drug the AE will be assigned (for example, due to partially missing dates), those AEs will be assigned to vilaprisan (conservative approach).

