6.4.2.4.2 Classifications of adverse events

Serious Adverse Events (SAEs) will be summarized in the same way as described for TEAEs.

Non-serious AEs will be shown on a summary table by primary SOC/PT.

Adverse events of special interest (AESI) will be identified in two different ways:

- 1) The investigators will assess all AEs to determine if they are AEs of special interest (AESIs) and document this in the eCRF. The following AEs are included:
 - a. HMB
 - b. Liver disorders
 - c. Endometrial disorders
 - d. Skin disorders
 - e. Adrenal disorders
- Adverse events will be categorized into AE groupings of special interest based on MedDRA groupings as defined within expert statement for compound vilaprisan (Selection of coding conditions applicable for AESIs as defined in the study protocols of vilaprisan phase II/III studies).

No.	AESI	Grouping
1	HMB (especially after end of treatment): HMB will be documented in detail throughout the study	MTG : [BMQ] Increased female genital bleeding[V8]
2	Liver enzymes	SMQ : Drug related hepatic disorders - comprehensive search (SMQ)[V29]
3	Endometrial hyperplasia (all subcategories according to WHO 2014 (and WHO 1994) classification	 PT selection: PT: Endometrial hyperplasia PT: Biopsy endometrium abnormal PT: Endometrial dysplasia PT: Endometrial metaplasia PT: Biopsy uterus abnormal
4	Endometrial thickening >18 mm	PT selection: PT: Endometrial thickening PT: Endometrial disorder

Table 6–2: List of AESIs in current expert statement based on MedDRA Version 22.1 (version 5.0, status 19FEB2020)

No.	AESI	Grouping
		PT: Endometrial hypertrophy
5	Adrenal neoplasms, Adrenal diagnoses related to cortical hyperfunction and cortical hypofunction	PBMQ : Adrenocortical gland pathology including tumors and related hormonal changes and conditions Vilaprisan (narrow scope)

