AESIs based on investigator assessment and AESIs based on MedDRA groupings will be presented separately. They will be presented by AESI group (if available), MedDRA primary SOC and PT and study drug. Summary tables for AESIs by maximum intensity and by worst outcome will be produced. Furthermore, listings will be provided.

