6.4.2.10 Findings resulting from adrenal monitoring

Subjects were asked to undergo scheduled adrenal monitoring at the safety closeout visit. The adrenal monitoring comprises the following assessments:

- Adrenal gland imaging
- Laboratory testing
- Signs and symptoms suggestive of hypercortisolism, hyperaldosteronism

All tables generated within this adrenal monitoring section will contain the absolute number of subjects and percentage among subjects who performed the safety closeout visit.

An *overview* table will be provided. This table includes the number and percentage of subjects taking part at the specific adrenal monitoring assessments. The following numbers and percentages of subjects will be provided in addition:

- Subjects with abnormal result in at least one of the assessments.
- Subjects with abnormal result for each specific assessment separately.
- Subjects for whom an external expert recommendation was obtained. Among those, also the number and percentage of subjects with any findings suspicious of an adrenal disorder and recommendation for further handling will be provided.
- Subjects who have seen a local specialist (including information on type of specialist).

Details of the *final diagnosis by the expert panel* will be provided in another table. This table contains the number and percentage of subjects assessed by an expert, subjects needed expert panel meeting, subjects where expert panel met, and subjects with at least one diagnosis by the expert panel. Among those, the following numbers and percentages of subjects will be provided:

- Subjects with agreement of the diagnosis among all three experts.
- Subjects with a specific diagnosis (multiple diagnoses are possible).

A listing of subjects with other diagnosis (i.e. diagnosis entered by the expert panel in a text field) will be provided. A listing of subjects with adrenal tumor will presented as well. It includes diagnosis, time from last study drug until date of panel assessment and possible causal relationship to study drug. Cases where the three experts did not agree on a diagnosis, are presented in a separate listing including also the diagnosis of the local specialist.

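### Skin closeout tables, and by default the adrenal ones, keep B1 as one column although it mixes placebo-only and vilaprisan-exposed women; AESI tables by study drug can file B2 events under placebo

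*SAP*

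**What the plan says.** - **Skin.** SAP 6.4.2.11: "Findings resulting from skin monitoring will be analyzed descriptively by treatment group".
- **Adrenal.** SAP 6.4.2.10 fixes the denominator, the "percentage among subjects who performed the safety closeout visit", but names no column variable. SAP 4.1 sets the general layout (A1, B1, B2), and Protocol 10.3.2.4 summarises safety variables by treatment group.
- **Sequences and pause.** Under Protocol 7.1, A1 is vilaprisan twice, B1 is placebo then vilaprisan, and B2 is vilaprisan then placebo. SAP 3 records that, from Amendment 4, women finished the period they were in and did not begin a further one.
- **AESIs.** SAP 6.4.2.4.2: "They will be presented by AESI group (if available), MedDRA primary SOC and PT and study drug". The assignment rule in 6.4.2.4.1 reads: "AEs with an onset at or after the start of TP2 will be assigned to the study drug taken during TP2". Where the assignment is unclear, for instance because of partial dates, the event goes to vilaprisan.
- **Event windows.** SAP 6.4.2.4 flags every AE as treatment-emergent unless it clearly began before first intake or "after the date of last study drug intake + 60 days (post-treatment AEs".
- **Post-treatment layout.** The only one stated is for ovarian-cyst AEs in SAP 6.4.2.2: "post-treatment AEs will be shown by treatment group (including pooled group A1+B2) only".
- **Other AE tables.** AEs are also described "by treatment group (including pooled treatment group A1+B2) separately for each treatment period". For serious events: "Serious Adverse Events (SAEs) will be summarized in the same way as described for TEAEs".

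**The concern.** Protocol section 3 gives the closeout programme two purposes: to support an analysis of human safety against the rodent tumour findings, and to help show whether vilaprisan contributes to such tumours. That question compares women who have taken vilaprisan with women who have not. Neither planned layout makes this comparison.

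In the group layout, the only column that can hold unexposed women is B1, and it also holds exposed ones. If past exposure carries risk, the B1 rate rises and the visible contrast shrinks. In the study-drug layout B1 is separated correctly, but B2 women who moved on to placebo carry their earlier vilaprisan exposure into the placebo column. Both effects push towards no difference, which is the result the sponsor expects to confirm. A reassuring table would therefore be open to question.

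**Working it through.** The plan states no figure on this point, so there is none to reproduce. The check traces each exposure history through the rules and then illustrates the size.

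**1. Exposure by group, among treated women given the drug they were randomised to**

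| Group | Started Period 2? | Ever took vilaprisan? | Group-layout column |
|---|---|---|---|
| A1 | either | yes | A1 |
| B2 | either | yes | B2 |
| B1 | yes | yes | B1 |
| B1 | no | no | B1 |

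The as-treated rule in SAP 5.1 deals with administration mistakes. It does not separate the last two rows.

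**2. Dilution in the B1 column**

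Let r be the risk in never-exposed women, R the true risk ratio, and f the share of B1 who started Period 2. The documents give neither R nor f. Assume that the vilaprisan exposure in B1 carries the same risk as that in A1 and B2.

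B1 risk = r(1 − f) + Rrf = r[1 + (R − 1)f], so the observed ratio = R / [1 + (R − 1)f].

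| | f = 0.10 | f = 0.25 | f = 0.50 |
|---|---|---|---|
| R = 3 | 3/1.2 = 2.50 | 3/1.5 = 2.00 | 3/2 = 1.50 |
| R = 2 | 2/1.1 = 1.82 | 2/1.25 = 1.60 | 2/1.5 = 1.33 |

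SAP 3 says too few women started Period 2 for valid conclusions. That does not fix f, so the low case belongs in the range.

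**3. Placebo column in the study-drug layout**

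Assume the same f in B1 and B2. The column then holds 52 B1 women (planned size, Protocol 10.4) and 52f B2 women already exposed to vilaprisan. The exposed share is f/(1 + f): 0.10/1.10 = 9%, 0.25/1.25 = 20% and 0.50/1.50 = 33%.

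**4. Timing of events found at closeout**

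Assume the last 84-day period began on 11 DEC 2018, the date of Amendment 4. It would end on 04 MAR 2019, and 60 days later is 03 MAY 2019. That is 201 days before Amendment 5 (20 NOV 2019), which introduced the adrenal and skin programmes. Detection at closeout therefore falls well after the 60-day window. This dates detection, not onset, and the SAP classifies by onset.

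| Event in a B2 woman who started Period 2 | Rule | Outcome |
|---|---|---|
| Recorded onset from Period 2 start to last intake + 60 days | 6.4.2.4.1 | placebo |
| Drug assignment unclear | 6.4.2.4.1, conservative rule | vilaprisan |
| No clear evidence of onset after + 60 days | 6.4.2.4 default | stays treatment-emergent |
| Clear onset after + 60 days | not stated whether a drug is assigned | by group only, if the ovarian-cyst layout is followed; placebo, if 6.4.2.4.1 is applied |

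**5. What a split could show**

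At the planned 52 per group (Protocol 10.4 says the total was not reached), never-exposed = 52(1 − f) and ever-exposed = 156 − never-exposed. With zero events, the one-sided 95% upper limit is 1 − 0.05^(1/n).

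| f | Never: n, limit | Ever: n, limit |
|---|---|---|
| 0.10 | 47, 6.2% | 109, 2.7% |
| 0.25 | 39, 7.4% | 117, 2.5% |
| 0.50 | 26, 10.9% | 130, 2.3% |

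**6. Exit biopsy**

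SAP 6.4.1.1 plans subgroups by treatment duration and windows by last treatment period. A placebo-only B1 woman has about 84 days (the 90-day-or-less class). A switched one has about 84 + 84 = 168 days (the 91 to 180 class). These women are largely separated already, apart from early stoppers.

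**The case against.** The strongest reply is that the plan already limits the problem:

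- The conservative rule and the treatment-emergent default protect events with uncertain onset.
- Adrenal tumours, malignant skin lesions, and atypical or malignant endometrial findings are SAEs. SAEs are tabulated by group and period as well as by drug, so treatment-emergent B2 events remain visible under B2.
- The adrenal-tumour listing and the skin narratives allow case review, which is the informative analysis for rare events.
- The TLF specification named in SAP 4.1 was not available and may add columns. The by-group layout of the adrenal tables is itself inferred.
- The never-exposed group would be small and non-randomised, whereas the group columns keep the allocation.

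Most of this stands and sets the limits of the point. It does not supply a table that counts skin or adrenal findings by vilaprisan exposure with a denominator. In addition, the adrenal-tumour listing gives time from last study drug, which is placebo for a B2 woman who started Period 2.

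A reader might infer that every late B2 event will be counted as placebo, or that every event found at closeout must be post-treatment. The documents do not support either. Both hold only if the detection date is recorded as the onset. A reader might also extend the point to exit biopsies, but SAP 6.4.1.1 already largely separates those women.

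**Conclusion.** The point holds as a weakness in presentation. For skin findings by the SAP's own words, and for adrenal findings by its default layout, B1 is one column of mixed exposure with no split planned in the SAP text. In the AESI tables by study drug, B2 events with a recorded onset at or after the start of Period 2 go to placebo despite earlier vilaprisan. The handling of post-treatment events by drug is left open.

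The size of the dilution cannot be derived. The range of 2.5 to 1.5 for a true ratio of 3 rests on assumed values of R and f and on equal risk after any vilaprisan exposure. These safety analyses are descriptive, so it would be wrong to read this as an error in a confirmatory result. It is a cheap improvement aimed at the stated purpose of the closeout data.

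**What to change.** 1. Add two descriptive columns to the skin and adrenal closeout tables, with the number of women in each: *ever took vilaprisan* (A1, B2, and B1 who started Period 2) and *never took vilaprisan* (B1 who did not).
2. Add the same columns to the endometrial, adrenal and skin AESI tables, including post-treatment events. Classify each event by whether any vilaprisan was taken before onset.
3. State in SAP 6.4.2.4.1 whether post-treatment AEs are assigned to a study drug.
4. Keep the period rule for ordinary AEs and for HMB and liver AESIs. Protocol 9.6.3.2.7 expects HMB to return after treatment, so an ever-exposed label would mislead there.
5. Exit-biopsy columns are optional.

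The cost is two columns and one sentence, from data already held. The downside is that the never-exposed group is small and non-randomised, because starting Period 2 depended on calendar time and on early stopping. The comparison must stay descriptive and be labelled so. If the TLF specification already has these columns, a cross-reference in the SAP is enough for items 1 and 2.

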6.4.2.12 Bleeding patterns per 28 days and per 84 days based on UF-DBD

The bleeding data recorded on the UF-DBD will be summarized using descriptive statistics in the SAF by treatment groups (including pooled treatment group A1+B2) using Intervals C and D. A reference period of 28 days will be used for most analyses, which corresponds to the Intervals D. When a reference period of 84 days is used, the Intervals D will be modified accordingly.

The bleeding intensity will be summarized by bleeding category using frequency tables by reference period of 28 days and 84 days.

The maximum bleeding intensity will be summarized using frequency tables by 28 days reference period.

The number of bleeding days will be analyzed by 28 days reference period and with the following bleeding categories:

- non-bleeding,
- spotting-only,
- bleeding (bleeding intensity of 'mild' or higher),
- bleeding including spotting (bleeding intensity of 'spotting' or higher),
- mild,
- moderate,
- severe,
- very severe.

An incomplete period which does not comprise 28 (or 84, respectively) days will be analyzed for any of the considered time periods of Intervals C. The analysis of this incomplete period is based on all subjects for whom the length of the considered time period is not a multiple of 28 (or 84, respectively) days. A subject's data from the last x < 28 (x < 84) days of the considered time period will be included.

7. Document history and changes in the planned statistical analysis

The following variables will be analyzed descriptively, even those were not listed as other efficacy/safety variables in the protocol:

- Percentage change in volume of the largest fibroid from baseline (measured by ultrasound)
- Percentage of subjects with a volume reduction of $\geq 25\%$ of the largest fibroid compared to baseline (measured by ultrasound)
- Uterine fibroid surgery performed during the study
- Bleeding patterns per 28 days and per 84 days based on UF-DBD

8. References

- [1] Best practice document RD-SOP-1107: Recording and Evaluation of Bleeding Data. Version 10.0
- [3] Upton GJ. Conditional independence, the Mantel-Haenszel test, and the Yates correction. The American Statistician. 2000 May 1;54(2):112-5.

Appendix 1: Menstrual pictogram (MP) mapping to menstrual blood loss volume (in mL)

During the study, subjects will be required to use selected types of sanitary products (pads and/or tampons), and to assess the intensity of their menstrual blood loss per sanitary product using a visual scoring system. The analysis value can be obtained from Table 9–1.

Sanitary product	Menstrual spot shape	Menstrual blood loss (mL)
always Ultra normal	Towel pictogram a	0.79
-	Towel pictogram b	1.51
	Towel pictogram c	3.08
	Towel pictogram d	4.64
	Towel pictogram e	6.75
	Towel pictogram f	11.91
always Ultra night	Towel pictogram a	0.74
	Towel pictogram b	2.20
	Towel pictogram c	4.21
	Towel pictogram d	6.84
	Towel pictogram e	9.42
	Towel pictogram f	15.2
always Ultra long	Towel pictogram a	1.36
	Towel pictogram b	1.89
	Towel pictogram c	3.68
	Towel pictogram d	6.12
	Towel pictogram e	8.69
	Towel pictogram f	13.41
o.b. Pro Comfort light	Tampon pictogram a	0.16
	Tampon pictogram b	0.55
	Tampon pictogram c	1.19
	Tampon pictogram d	2.98
o.b. Pro Comfort regular	Tampon pictogram a	0.35
	Tampon pictogram b	1.31
	Tampon pictogram c	2.09
	Tampon pictogram d	5.66
o.b. Pro Comfort super	Tampon pictogram a	1.29
	Tampon pictogram b	1.87
	Tampon pictogram c	3.49
	Tampon pictogram d	9.37
o.b. Pro Comfort super plus	Tampon pictogram a	1.34
	Tampon pictogram b	3.36
	Tampon pictogram c	5.81
	Tampon pictogram d	12.23
Tampax light	Tampon pictogram a	1.24
	Tampon pictogram b	1.52
	Tampon pictogram c	1.73
	Tampon pictogram d	3.10
Tampax regular	Tampon pictogram a	0.63
	Tampon pictogram b	1.58
	Tampon pictogram c	2.20
	Tampon pictogram d	5.62

Table 9–1: Mapping of the menstrual pictogram (MP) to menstrual
blood loss

Sanitary product	Menstrual spot shape	Menstrual blood loss (mL)
Tampax super	Tampon pictogram a	1.29
	Tampon pictogram b	2.38
	Tampon pictogram c	4.01
	Tampon pictogram d	7.76
Tampax super plus	Tampon pictogram a	1.20
	Tampon pictogram b	2.56
	Tampon pictogram c	4.98
	Tampon pictogram d	9.49
Other Tampon	Tampon pictogram a	3.55
	Tampon pictogram b	4.33
	Tampon pictogram c	6.25
	Tampon pictogram d	8.30

Table 9–1: Mapping of the menstrual pictogram (MP) to menstrual blood loss

